2 INTRODUCTION

Racecadotril (acetorphan), an enkephalinase inhibitor, represents a promising approach to the treatment of diarrhoea. Water and electrolyte transport in the intestinal mucosa is regulated by local messengers (neuropeptides, amines, and eicosanoids). Most of them act via the mediation of cyclic adenosine monophosphate (cAMP), activating or inhibiting its production from adenosine triphosphate. An increase in cAMP is induced by endogenous (e.g. VIP, PGE₂) or exogenous agents (e.g. *V. cholerae*, *E. coli* toxins) and leads to net hypersecretion of water and electrolytes. Opiate neuropeptides are localized in the intestine myenteric and submucosal plexuses, where they modulate motility (mu receptors) and secretion (delta receptors). Activation of mu receptors prolongs intestinal transit while activation of delta receptors reduces intestinal secretion of water and electrolytes. Enkephalins activate delta receptors and inhibit adenylyclase, thus facilitating a decrease in cAMP levels with a consequent reduction in water and electrolyte secretion. This antisecretory action, however, is brief because enkephalins are rapidly degraded by the membrane peptidase enkephalinase (EC 3.4.24.11). Racecadotril is a prodrug that is rapidly hydrolysed in man into the active metabolite thiorphan, which is a powerful and selective enkephalinase inhibitor. Thus, the antisecretory action of enkephalins is prolonged in the presence of thiorphan. Furthermore, unlike opiates and loperamide, Racecadotril does not act on mu receptors and therefore it does not prolong intestinal transit, nor does it favour bacterial growth in the small intestine.

Racecadotril is devoid of any central or peripheral nervous side effect, at the opposite of opiates, such as respiratory depression or inhibition of intestinal transit.

The trade names are Tiorfan® in France, where it has been approved in capsules since July 1992 and launched in March 1993, and Hidrasec® in other countries. Pediatric dosage form of racecadotril (Tiorfan® sachet 10 mg and 30 mg) were approved in France in October 1999. Hidrasec® capsules were registered in Russia for adult use in 2017. The products are currently approved in 85 countries.

Diarrhea is defined as the passage of unusually loose or watery stools, with a frequency of at least three times in a 24 hour period. The objective for treatment of acute diarrhea associated symptoms is to prevent and treat dehydration at first, to prevent nutritional damage and to reduce the duration and severity of diarrhea. Antidiarrheal drugs have been developed to prevent dehydration and to resolve diarrhea on top of with oral rehydration solution (ORS). Ideally antidiarrheals have a positive safety profile and have limited or no effects on motility and basal intestinal secretion.

Racecadotril has been shown to be effective and well tolerated for the complementary symptomatic treatment of acute diarrhea in pediatric subjects older than 3 months.

This study is conducted to assess the efficacy and safety profile of Racecadotril in Russia pediatric and adolescent subjects.

The dosing regimen of Racecadotril is 1.5 mg/kg 3 times daily, via the oral route resulting in the following instruction:

In infants less than 9 kg: one 10 mg sachet 3 times daily.

In infants from 9 kg to < 13 kg: two 10 mg sachets 3 times daily.

In children from 13 kg to 27 kg: one 30 mg sachet 3 times daily.

In children of more than 27 kg: two 30 mg sachets 3 times daily.

In children or adolescents of 60 kg or higher: 100 mg capsule 3 times daily

3 STUDY OBJECTIVES

3.1 Primary Objective(s)

The primary objective is to evaluate the efficacy of Racecadotril in addition to standard treatment oral rehydration solution (ORS) versus ORS alone in infants, children and adolescents (3 months until <18 years) with acute diarrhea measured as duration of diarrhea (hours) between the start of treatment until final diarrheal/watery stool before recovery or end of study treatment (treatment duration maximal 5 days).

Duration of diarrhea is defined by date and time of the evacuation of the final watery/diarrheal stool before recovery derived from the daily diary.

3.2 Secondary Objective(s)

- Number of recovered subjects per treatment group in total and until each individual treatment day. Mean and median time until recovery per treatment group.
- Time until recovery, defined by date and time of the evacuation of the first of two consecutive normal stools or no stool within 12 hours.
- Global Physician Assessment at the end of treatment:
 - 1 = Complete relief of acute diarrhea,
 - 2 = marked improvement of acute diarrhea,
 - 3 = moderate improvement of acute diarrhea,
 - 4 = slight improvement of acute diarrhea,
 - 5 = no change in acute diarrhea,
 - 6 = worsening of acute diarrhea. (Treatment success = GPA score of 1 or 2).
- For toilet trained children and adolescents: number of stools per day as well as number of watery stools per day from start of treatment and until end of study treatment.

3.3 Safety Objective(s)

To evaluate the safety and tolerability of Racecadotril together with oral rehydration solution (ORS) versus ORS alone in infants, children and adolescents with acute diarrhea by adverse events, physical examination and vital signs.

4 STUDY DESIGN

4.1 Overall Study Design and Plan-Description

This is a controlled, open-label, parallel-group study evaluating the efficacy and safety of Racecadotril in infants, children and adolescents with acute diarrhea. The number of subjects to be screened is 150 in order to enroll 124 subjects for either standard treatment (oral rehydration solution, ORS) alone or ORS plus Racecadotril.

1.5 mg/kg of Racecadotril will be administered, 3 times daily, via the oral route. Study drug intake will start either with the noon or the evening dose on day 1.

In infants less than 9 kg: one 10 mg sachet 3 times daily.

In infants from 9 kg to <13 kg: two 10 mg sachets 3 times daily.

In children from 13 kg to 27 kg: one 30 mg sachet 3 times daily.

In children of more than 27 kg: two 30 mg sachets 3 times daily.

In children or adolescents of 60 kg or higher: 100 mg capsule 3 times daily

Standard treatment is oral rehydration solution (ORS) according to the registered local label and the instruction of the investigator. The same brand of ORS and the same age-appropriate standardized treatment pattern for the subjects will be applied throughout the trial. ORS treatment and dosing will be documented in the CRF.

Screening and Enrolment (Day 1, Visit 1)

Subjects presenting with acute diarrhea will be evaluated for eligibility. They will undergo a physical examination including assessment of dehydration level, vital signs, a review of their medical history and concomitant medication. If the subjects are eligible for the study, demographics, number of stools during the last 24 hours will be assessed as baseline values. The subjects will be randomized to Racecadotril plus ORS or ORS alone. On Day 1 the subject will start with study treatment. The starting dose will either be the noon or the evening dose depending on the timing of Visit 1.

Treatment period (until recovery, maximally 5 days)

Subjects will be treated with Racecadotril tid according to the body weight dose requirement on an in- or out-patient basis for maximum 5 days. One arm will be treated with ORS alone as standard treatment, the other treatment arm will be treated with ORS (according to the registered local label and the instruction of the investigator) in addition to Racecadotril. ORS will be prescribed by the investigator and will be taken according to the product label and the instruction of the investigator. The parent(s)/caregiver(s) will be instructed to stop study drug treatment when the patient recovered. On each day, the parent(s)/caregiver(s) will fill in their diaries, documenting the date and time of each individual stool, the stool consistency of each stool (diarrheal/watery or normal), the amount of ORS and the study drug intake. After the occurrence of two consecutive normal stools, the parent(s)/caregiver(s) can stop recording of the diary and

[figure not shown]
return to the study site for the end of treatment visit. The date of recovery is the day when the first of two consecutive normal stools were excreted. AEs are to be reported on an ongoing basis.

End of treatment (Day 6 or early recovery, Visit 2)

The last dose of study drug will be the morning dose of day 6, if not recovered earlier. The same day, or within 24 hours after recovery, the parent(s)/caregiver(s) will visit the site for the end of treatment visit of the child. Data on vital signs, AEs, physical examination and concomitant medication will be collected. Subjects will return their diaries and unused medication.

Safety follow-up

A phone call will be performed at 5-7 days after end of the treatment period for the safety follow-up.

4.2 Discussion of Study Design, Including the Choice of Control Groups

Standard treatment for pediatric subjects with acute diarrhea is ORS and adequate rehydration is also the basic treatment regimen for adolescents. ESPGHN guidelines (Guarino et al. 2014) and World Gastroenterology Organization (WGO) guidelines 2012 state that the gold standard of treatment of acute diarrhea in pediatric population is oral rehydration solution (ORS). Thus ORS is considered to be the appropriate control treatment for planned investigation.

An open-label design of Racecadotril on top of ORS versus ORS alone is appropriate as the primary endpoint can be measured objectively: duration of diarrhea (hours) between the start of treatment until final diarrheal/watery stool before recovery or end of study treatment.

5 SELECTION OF STUDY POPULATION

5.1 Inclusion Criteria

- Informed Consent:
 - For all subjects: signed informed consent from one of the parent(s)/caregiver(s)
 - For subjects ≥ 14 years of age: signed informed assent form in addition to parent's written informed consent
 - For subjects <14 years of age: verbal assent if age and ability allows
- Children and adolescents, both genders, age from 3 months to < 18 years of age.
- Confirmed diagnosis of acute diarrhea (defined as the passage of three or more unformed or liquid stools within the last 24 hours and lasting for less than three days).
- Females of child-bearing potential should agree to continue using a medically acceptable method of birth control throughout the study and for 30 days immediately after the last dose of study drug. Medically acceptable methods of birth control include bilateral tubal ligation or the use of either a contraceptive implant, a contraceptive injection, an intrauterine device, or an oral contraceptive taken within the past three months where the subject agrees to continue using during the study or to adopt another birth control method, or a double-barrier method which consists of a combination of any two of the following: diaphragm, cervical cap, condom, or spermicide.

5.2 Exclusion Criteria

- Known allergy to Racecadotril or any of its ingredients.
- Subjects suffering from renal or hepatic impairment.
- Subjects who need treatment for diarrhea other than ORS alone.
- Subjects with fever > 39 degrees Celsius.
- Subjects with bloody and/or purulent stools.
- Subjects suffering from antibiotic-associated diarrhea, chronic diarrhea or iatrogenic diarrhea.
- Subjects with alternating bouts of diarrhea and constipation.
- Diarrhea due to exacerbation of chronic gastrointestinal diseases such as irritable bowel syndrome, inflammatory bowel disease or pancreatic exocrine insufficiency.
- Cystic fibrosis or coeliac disease.
- Subjects suffering from prolonged or uncontrolled vomiting.
- Subjects with rare hereditary problems of fructose or galactose intolerance, Lapp lactase deficiency, glucose-galactose malabsorption syndrome or sucrase isomaltase insufficiency or primary or secondary lactase insufficiency.
- Subjects having received antibiotic treatment at any time within 30 days prior to inclusion into the study.
- Subjects having received antidiarrheal drugs 48 hours prior to inclusion into the study.
- Subjects with severe dehydration required for intravenous/parenteral rehydration.

- Subjects who have reported angioedema with angiotensin converting enzyme inhibitors (such as captopril, enalapril, lisinopril, perindopril, ramipril)
- Subjects with combined diseases or medical situations that would prevent to be enrolled depending in the judgment of the investigator.
- Intake of experimental drug within 30 days prior to study start.
- Subjects with contraindications to ORS or for whom warnings/precautions of ORS apply.
- Adolescents (≥ 60 kg) not able to swallow capsules
- Pregnancy or lactation

6 REMOVAL OF SUBJECTS FROM THERAPY OR ASSESSMENT

All subjects are free to withdraw from participation in this study at any time, for any reason, specified or unspecified, and without penalty or loss of benefits to which the subject is otherwise entitled.

The Study Termination form must be completed for all subjects who did not fail screening, those who completed and those who prematurely terminated the study.

In case of premature termination of the subject from the study, the primary reason for this premature termination is to be indicated according to the following definitions:

- Adverse event: discontinuation due to any adverse event (AE) with a corresponding entry reflected on the Adverse Events form in the CRF.
- Lack of efficacy: subject fails to respond to the study drug at an acceptable level where the subject or the Investigator feels it is in the best interests of the subject to seek another treatment.
- Lost to follow-up: the subject fails to return to the study site for scheduled visits and does not respond to telephone or written attempts to contact.
- Withdrew consent: subject decides to stop his/her participation in the study for any reason other than an AE, or is unable to complete the study as described in the clinical study protocol (e.g. subject is relocating to another location).
- Administrative: the Sponsor decides to discontinue the study (either at the study site or the entire study), e.g. general safety problems leading the Sponsor to entirely stop the study.
- Protocol violation – anything which is in direct violation of the clinical study protocol (e.g. inclusion/exclusion violation).

Subjects with two consecutive temperature measurements of > 39 degrees Celsius during the study should be withdrawn from the study for further diagnosis and alternative treatments. Also subjects whose disease state worsens, e.g. dehydration or increased vomiting, should be withdrawn from the study. An end of treatment visit will be performed.

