7.7 Prior and Concomitant Therapy

During the study, participants are not allowed to be treated with the following treatments in addition to the study drug:

- Antiperistaltic drugs, e.g. loperamide,
- Antibiotics
- Antipyretics
- Intestinal antiseptics, e.g. 8-hydroxyquinoline
- Respiratory decongestants, e.g. phenylephrine
- Antitussive medication, e.g. noscapin
- Absorbents, e.g. diosmectite, charcoal, pectin, psyllium
- Zinc-containing medication
- Homemade ORS
- ACE Inhibitors
- Antispasmodics
- Drugs for symptomatic treatment of diarrhea, e.g. pancreatic enzymes, anticholinergic drugs, opiates, diphenoxylate.

Subjects on continuous probiotic treatment (e.g. Lactobacillus, Bifidobacterium, yeast) or probiotic-containing supplements/formula of the same product/brand for at least 4 weeks prior to study start can be included.

The presence of bloody or purulent stool and fever may indicate either the presence of invasive bacteria as a reason for diarrhea or the presence of another severe disease, warranting causal (e.g. antibiotic) treatment or further investigation. In addition, Racecadotril has not been investigated in patients with antibiotic-associated diarrhea. Therefore, Racecadotril should not be administered under these conditions.

Subjects who need treatment with the above listed medication should be withdrawn from the study.

Dietary modifications for thickening of the stools are allowed.

Any intake of other medication is allowed as judged appropriate by the Investigator except those on the list of prohibited medications above.

All medication taken by the subject during the study (from signing the informed consent form through post-study follow-up) is to be recorded on the Concomitant Medication form, except for study drug.

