8.3 Other Assessments

Informed Consent

Voluntary written informed consent must be obtained from one parent(s)/caregiver(s) (or their legally acceptable representative) prior to performing any study-related procedures (see Section 1.3) for all subjects. For subjects < 14 years voluntary verbal assent will be obtained if age and ability allows in addition.

Voluntary written informed assent will be obtained from subjects \geq 14 years of age in addition to parent's written informed consent prior to performing any study-related procedures (see Section 1.3).

Demographic Data

Demographic data (gender, date of birth, race) will be collected for all subjects.

Medical History

Any clinical event, including diagnosis, condition, or surgery, that occurred prior to allocation to treatment, is to be recorded on the Medical History form. In case a clinical event concerns a chronic disorder, which means it started in the past and it is still present at the screening visit, it should also be recorded on the Medical History Form. Examples of these events are diabetes, migraine, and hay fever.

Concomitant Medication

All medication taken by the subject during the study (from signing the informed consent form through post-study follow-up) is to be recorded on the Concomitant Medication form, except for study drug.

Subject Diary

The parent(s)/caregiver(s) have to document date and time of each individual stool of the subject and the stool consistency (watery, normal) of each evacuation continuously. The subject individual stool consistency before start of the diarrhea is defined as normal (e.g. taking into account the age and diet, e.g. breast feeding, of the individual subject). Recording can be stopped after the excretion of two consecutive normal stools.

The date, time and dose of study drug intake as well as the amount ORS and other liquids (e.g. water, milk formula) consumed has to be recorded.

Fever will be measured once daily by the parent(s)/caregiver(s) and documented in the diary including method, time and value.

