8.6 Flow Chart of Study Assessments

All study assessments will be conducted as indicated in Table 1, which displays the frequency and timing of all measurements.

Table 2: Flow Chart of Study Assessments

Note: Any additional medical procedures not included into this study protocol can be performed within routine clinical practice in each medical institution

Period	Screening	End of Treatment period	Safety follow-up (phone call 5-7 days after Visit 2)
Visit	1	2	3
Day	1	6²	11-13
Informed consent	X		
Randomization	X		
Demographic data	X		
Medical history	X		
Pregnancy Test ⁴	X		
Physical examination ³	X	X	

In- or outpatient	X		
Stool frequency within the last 24 hours	X		
Inclusion/exclusion criteria	X		
Vitals signs	X	X	
Dispense study drug	X		
Concomitant medication	X	X	X
Compliance check		X	
Adverse events	X	X	X
Collect study drug		X	
Dispense diary	X ¹		
Collect diary		X	

¹ Subjects' parent/caregivers have to fill in their daily diaries continuously.

² or within 24 h after recovery if this occurs before day 6

³ including assessment of dehydration level

⁴ for females of child-bearing potential, urine test

9 ADVERSE EVENTS**9.1 Adverse Events**Definition of Adverse Event

Any untoward medical occurrence in a patient or clinical investigation subject administered a pharmaceutical product and which does not necessarily have a causal relationship with this treatment. An AE can therefore be any unfavorable and unintended sign (including an abnormal laboratory finding, for example), symptom (including an AE occurring from drug abuse, an AE occurring from drug withdrawal and any failure of expected pharmacological action), or disease temporally associated with the use of a pharmaceutical product, whether or not considered related to the pharmaceutical product.

An elective surgery/procedure scheduled to occur during a study will not be considered an adverse event if the surgery/procedure is being performed for a pre-existing condition and the surgery/procedure has been pre-planned prior to study entry. However, if the pre-existing condition deteriorates unexpectedly during the study (e.g. surgery performed earlier than planned), then the deterioration of the condition for which the elective surgery/procedure is being done will be considered an adverse event.

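### For out-patients, the fever rule needs two consecutive readings > 39 °C but one a day is scheduled, so on that schedule it is met about a day after the first, with no prompt to call the site

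*Protocol*

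**What the plan says.** Section 6 of the protocol sets the fever rule: "Subjects with two consecutive temperature measurements of > 39 degrees Celsius during the study should be withdrawn from the study". It gives the purpose in the same sentence: such children "should be withdrawn from the study for further diagnosis and alternative treatments". It sets no interval between the two readings and asks for no repeat after a first high one.

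The Subject Diary paragraph of section 8.3 sets the measurement schedule: "Fever will be measured once daily by the parent(s)/caregiver(s) and documented in the diary including method, time and value". The time of day is recorded but not fixed. Section 8.2 does not list temperature among the vital signs taken at the site.

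Section 4.1 allows out-patient treatment. The flow chart in 8.6 shows no contact between Visit 1 and Visit 2, and the diary is collected at Visit 2. For a child who has not recovered, Visit 2 falls on Day 6, the day of the last dose. Otherwise it follows recovery: "The same day, or within 24 hours after recovery, the parent(s)/caregiver(s) will visit the site for the end of treatment visit".

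The other provisions that bear on a febrile child are:
- Section 6, worsening: "Also subjects whose disease state worsens, e.g. dehydration or increased vomiting, should be withdrawn from the study".
- Section 7.7, which puts antipyretics and antibiotics on the prohibited list and adds: "Subjects who need treatment with the above listed medication should be withdrawn from the study".
- Section 4.1: "AEs are to be reported on an ongoing basis".
- The note above the flow chart in 8.6: "Any additional medical procedures not included into this study protocol can be performed within routine clinical practice in each medical institution".

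**The concern.** The rule counts readings, but the schedule supplies only one reading a day. If a family does exactly what the protocol asks and no more, a first reading > 39 °C triggers nothing under the fever rule. The next day's reading has to be high as well before it applies. During that interval sections 6 and 8.3 neither ask the caregiver to measure again nor tell the caregiver to contact the site, and the site does not see the diary.

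What is at stake is patient safety. The trial treats out-patients from 3 months of age. The step the rule exists to start, namely diagnosis and other treatment, begins about a day after the first high reading if only scheduled readings are used. In the active arm dosing can continue meanwhile. A two-day confirmation may be intended as a test for sustained fever, but nothing in the protocol says so. As written, the wait is a by-product of the diary schedule.

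**Working it through.** The plan states no figure for this delay, so there is nothing to reproduce. The check is schedule arithmetic.

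**Inputs from the protocol**
- Readings needed: 2 consecutive, each > 39 °C (section 6).
- Scheduled readings: 1 a day, clock time not fixed (8.3).
- Doses: 3 a day, the first at noon or in the evening of Day 1, the last on the morning of Day 6 (4.1).
- Fever > 39 °C excludes at entry (5.2), so an eligible child's entry reading cannot be the first of the pair.

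**Total doses.** Noon start: 2 + 4 × 3 + 1 = 15. Evening start: 1 + 4 × 3 + 1 = 14.

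**Constant clock time.** Delay = (2 − 1) × 24 h = 24 h. Doses in between = 3, out of at most 14 or 15. This holds whatever the hour of measurement.

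**Range when the hour varies.** The documents fix no hours. I assume readings between 07 and 20 h and doses at 08, 13 and 19 h.
- First high reading on Days 2 to 4. Shortest gap: 20 h to 07 h next day = 11 h, 0 doses. Longest gap: 07 h to 20 h next day = 37 h, 6 doses.
- First high reading on Day 1, noon start. Shortest gap: 11 h, 0 doses. Longest gap: 13 h to 20 h next day = 31 h, 4 doses.
- First high reading on Day 1, evening start. Shortest gap: 11 h, 0 doses. Longest gap: 19 h to 20 h next day = 25 h, 3 doses.
- A first high reading on Day 5 is left out: its scheduled confirmation falls on Day 6, when treatment ends and Visit 2 takes place.

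Narrowing the assumed reading window to 08 to 20 h changes the range on Days 2 to 4 to 12 to 36 h. The centre stays at 24 h.

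The dose counts apply to the Racecadotril arm only. In the control arm there is no study drug, so only the delay applies.

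**The case against.** The strongest reply is that the two-reading rule is not what stands between a sick child and a doctor. Four other exits need no second reading:
- Under 7.7, a child judged to need an antipyretic or an antibiotic must be withdrawn. An antipyretic is a fever treatment, so this exit is fever-linked and could act at the first high reading.
- Section 6 withdraws a child whose disease worsens.
- Section 9.1.1 treats any change in medical status after allocation as an adverse event, which a new high fever would be, and section 6 allows discontinuation for any adverse event.
- The family may withdraw at any time.

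Section 7.7 also has a paragraph that names fever alongside bloody or purulent stool as a possible sign of invasive infection or other severe disease, and says Racecadotril should not be given in those conditions. Further, an unscheduled repeat is not forbidden and would count, two daily readings are a reasonable way to separate sustained fever from a spike or a measurement error, and caregiver instructions outside these documents may already contain a call step.

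Most of this stands, and it limits the point. A reader might infer that a febrile child has no way out of the trial for a day, or that the protocol forbids earlier diagnosis. The exits above rule that out. What they leave untouched is the timing of the fever rule itself. The 7.7 exit depends on someone judging that treatment is needed, and sections 6 and 8.3 do not tell the caregiver to consult anyone after a high reading. The worsening rule does not list fever among its examples. The 7.7 paragraph supports prompt investigation, but it can be read as fever together with blood or pus and so may not cover fever alone. The repeat is permitted but not requested, so how fast the rule acts depends on the family. Caregiver materials cannot be assessed here; the point is confined to sections 6 and 8.3.

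**Conclusion.** The point holds as a cheap patient-safety improvement. For out-patients on scheduled readings alone, the fever rule is met about one day after the first reading > 39 °C: 24 h and 3 Racecadotril doses at a constant clock time, or 11 to 37 h and 0 to 6 doses on Days 2 to 4 under the assumed hours. This presumes that the next day's reading is also high and that nobody takes an unscheduled repeat. The two-reading rule is the latest mandatory exit for a child with persistent high fever, and other exits may well act first.

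How many children this would affect cannot be derived: the documents give neither the out-patient share nor the frequency of fever > 39 °C during treatment. A reader might also infer that the delay biases the comparison of the arms. The documents give no basis for that, and no effect on the efficacy result is claimed.

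**What to change.** In 8.3 and section 6, require the caregiver to repeat any reading > 39 °C on the same day, after an interval set by the sponsor's medical lead, and to phone the site that same day. Section 6 then acts on that pair of readings. The 39 °C threshold stays as it is. If the sponsor prefers to keep two daily readings in order to identify sustained fever, section 6 should say so, and the same-day phone call after the first high reading should still be required. Stating the intention without the call would not bring the site in any earlier.

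The change needs two or three sentences and a line in the diary instructions, with no new visit. The costs are slight caregiver burden and some earlier or additional withdrawals. SAP 4.2.1 censors every subject without an event at 144 hours, so a withdrawal brought forward by a day leaves that child's primary record unchanged unless recovery would have come in between. An additional withdrawal (high on the repeat, not high the next day) can replace an event with a censored time. It also uses part of the drop-out allowance in Protocol 10.8: 55 / 0.9 = 61.1, which the plan takes as 62, leaving 62 − 55 = 7 per group and 14 in all. One such child is 1/14 = 7.1% of that allowance. As an illustration only, five would be 5/14 = 35.7% of it, or 5/124 = 4.0% of the trial.
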